## 2 Schedule of Study Assessments \*

Procedure	All visits/assessments may be scheduled $\pm$ 3 business days										
	Screening  <math>\leq</math> 28 days from Baseline (First day drug administration)	Cycle 1	Cycles 2 - 3	Cycle 4 				Cycles 5-12	Lenalidomide Maintenance Therapy	Discontinuation From Protocol Therapy 	Follow- Up Phase
	Days 1, 8, 15, and 22	Days 1, and 15	Day 1	Day 3 or 4 at investigator discretion	Day 8	Day 15	Day 22	Day 1 and 15			
Study drug administration **		X	X	X					X	X	
Record prior medications, treatments	X										
Record prior anti-cancer therapies	X										
Physical examination, vital signs, weight	X	X 	X 	X 					X 		
ECOG performance status	X	X 	X 	X 					X 		
ECG	X										
Assess lymphadenopathy, spleen / liver 		X 	X 	X 		X 	X 		X 		
Peripheral blood for , ZAP 70, $\beta$ -2 microglobulin, and IgHV mutational status 	X										
Research samples 	X			X							
Baseline lesion assessment	X			X							
Bone marrow 	X			X					X	X	X 
CT of the neck, chest, abdomen & pelvis 	X			X					X		X 
Hematology 	X	X	X	X 		X 	X 	X 	X 	X 	
Serum chemistry 	X	X	X	X 	X 	X 	X 	X 	X 	X 	
Hepatitis B and C serology, HBV DNA PCR 	X 										
Pregnancy testing 	X			X		X	X	X	X		
Register patient into REMS® program	X										

Prescribe lenalidomide via REMS 				X				X			
Record adverse events 		X	X	X				X	X 		
Record concomitant therapies/procedures		X	X	X				X			
Obtain Follow-Up anti-cancer treatments											X
Obtain Follow-Up survival information											X

\* An unscheduled visit can occur at any time during the study. Source must be maintained for these unscheduled visits. The date for the visit and any data generated must be recorded on the appropriate CRF. Source documents for these unscheduled visits must also be maintained.

\*\* See Table 1 for detailed study drug administration schedule.

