 Pregnancy test for females of childbearing potential. A female of childbearing potential (FCBP) is a sexually mature female who: 1) has not undergone a hysterectomy or bilateral oophorectomy; or 2) has not been naturally postmenopausal for at least 24 consecutive months (i.e., has had menses at any time in the preceding 24 consecutive months). Pregnancy tests must occur within 10 – 14 days and again within 24 hours prior to prescribing lenalidomide for Cycle 1 (prescriptions must be filled within 7 days). FCBP with regular or no menstruation must have a pregnancy test weekly for the first 28 days and then every 28 days while on lenalidomide therapy (including breaks in therapy); at discontinuation of lenalidomide and at Day 28 post the last dose of lenalidomide. Females with irregular menstruation must have a pregnancy test weekly for the first 28 days and then every 14 days while on lenalidomide therapy (including breaks in therapy), at discontinuation of lenalidomide and at Day 14 and Day 28 post the last dose of lenalidomide (see Appendix: Risks of Fetal Exposure, Pregnancy Testing Guidelines and Acceptable Birth Control Methods).

 Adverse event data entry will be captured on day 1 of each cycle. An additional safety assessment will be done 28 days (+/- 2 days) following the last dose of protocol therapy.

 If physical examination, vital signs, weight and ECOG performance status were done within 7 days of Day 1, they do not need to be repeated on Day 1. During cycle 1 the physical examination will be done on day 1 and day 15. On subsequent cycles it will be done on day 1 only.

 Lenalidomide must be prescribed through and in compliance with the REMS® program of Celgene Corporation. Prescriptions must be filled within 7 days. Consideration should be given to prescribing lenalidomide 5 to 7 days in advance of Day 1 of each cycle to allow time for required patient and prescriber surveys, and drug shipment to patient. Any unused Revlimid® (lenalidomide) should be returned to the patient for disposition in accordance with the REMS® program.

 Any required screening tests that have been performed as standard of care prior to consent and are within 28 days of starting study treatment may be used for screening and do not need to be repeated. A bone marrow biopsy performed within 6 weeks of starting study treatment does not need to be repeated during screening.

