9. Disease free of prior malignancies for  $\geq$  5 years with exception of currently treated basal cell, squamous cell carcinoma of the skin, or carcinoma "in situ" of the cervix or breast.

10. All study participants must be registered into the mandatory REMS® program, and be willing and able to comply with the requirements of REMS®.

11. Females of childbearing potential (FCBP)† must have a negative serum or urine pregnancy test with a sensitivity of at least 50 mIU/mL within 10 – 14 days and again within 24 hours prior to prescribing lenalidomide for Cycle 1 (prescriptions must be filled within 7 days) and must either commit to continued abstinence from heterosexual intercourse or begin TWO acceptable methods of birth control, one highly effective method and one additional effective method AT THE SAME TIME, at least 28 days before she starts taking lenalidomide. FCBP must also agree to ongoing pregnancy testing. Men must agree to use a latex condom during sexual contact with a FCBP even if they have had a successful vasectomy. See Appendix A: Risks of Fetal Exposure, Pregnancy Testing Guidelines and Acceptable Birth Control Methods.

---

† A female of childbearing potential is a sexually mature female who: 1) has not undergone a hysterectomy or bilateral oophorectomy; or 2) has not been naturally postmenopausal for at least 24 consecutive months (i.e., has had menses at any time in the preceding 24 consecutive months).

---

12. Able to take aspirin (81 or 325 mg) daily as prophylactic anticoagulation (patients intolerant to ASA may use warfarin or low molecular weight heparin).

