#### Contraception

Females of childbearing potential (FCBP) enrolled in this protocol must agree to use two reliable forms of contraception simultaneously or to practice complete abstinence from heterosexual intercourse during the following time periods related to this study: 1) for at least 28 days before starting lenalidomide; 2) throughout the entire duration of lenalidomide treatment; 3) during dose interruptions; and 4) for at least 28 days after lenalidomide discontinuation.

The two methods of reliable contraception must include one highly effective method and one additional effective (barrier) method. FCBP must be referred to a qualified provider of contraceptive methods if needed. The following are examples of highly effective and additional effective methods of contraception:

- Highly effective methods:
  - Intrauterine device (IUD)
  - Hormonal (birth control pills, injections, implants)
  - Tubal ligation
  - Partner's vasectomy
- Additional effective methods:
  - Male condom
  - Diaphragm
  - Cervical Cap

---

Because of the increased risk of venous thromboembolism in patients with multiple myeloma taking lenalidomide and dexamethasone, combined oral contraceptive pills are not recommended. If a patient is currently using combined oral contraception the patient should switch to one of the effective method listed above. The risk of venous thromboembolism continues for 4–6 weeks after discontinuing combined oral contraception. The efficacy of contraceptive steroids may be reduced during co-treatment with dexamethasone.

Implants and levonorgestrel-releasing intrauterine systems are associated with an increased risk of infection at the time of insertion and irregular vaginal bleeding. Prophylactic antibiotics should be considered particularly in patients with neutropenia.

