**Before starting lenalidomide**

*Female Patients:*

FCCP must have two negative pregnancy tests (sensitivity of at least 50 mIU/mL) prior to prescribing lenalidomide. The first pregnancy test must be performed within 10-14 days prior to prescribing lenalidomide and the second pregnancy test must be performed within 24 hours prior to prescribing lenalidomide. The patient may not receive lenalidomide until the Investigator has verified that the results of these pregnancy tests are negative.

*Male Patients:*

Must agree to practice complete abstinence or agree to use a condom during sexual contact with pregnant females or females of childbearing potential throughout the entire duration of lenalidomide treatment, during dose interruptions and for at least 28 days following lenalidomide discontinuation, even if he has undergone a successful vasectomy.

Amendment 5 Dated 03/02/2016

**During study participation and for 28 days following lenalidomide discontinuation***Female Patients:*

- FCBP with regular or no menstrual cycles must agree to have pregnancy tests weekly for the first 28 days of lenalidomide treatment, including dose interruptions and then every 28 days throughout the remaining duration of lenalidomide treatment, including dose interruptions, at lenalidomide discontinuation, and at Day 28 following lenalidomide discontinuation. If menstrual cycles are irregular, the pregnancy testing must occur weekly for the first 28 days of lenalidomide treatment, including dose interruptions, and then every 14 days throughout the remaining duration of lenalidomide treatment, including dose interruptions, at lenalidomide discontinuation, and at Day 14 and Day 28 following lenalidomide discontinuation.
- At each visit, the Investigator must confirm with the FCBP that she is continuing to use two reliable methods of birth control at each visit during the time that birth control is required.
- If pregnancy or a positive pregnancy test does occur in a study patient, lenalidomide must be immediately discontinued.
- Pregnancy testing and counseling must be performed if a patient misses her period or if her pregnancy test or her menstrual bleeding is abnormal. Lenalidomide treatment must be temporarily discontinued during this evaluation.
- Females must agree to abstain from breastfeeding during study participation and for at least 28 days after lenalidomide discontinuation.

*Male Patients:*

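### Contraception and scheduled post-screening pregnancy tests are timed only from lenalidomide, so 6 of 8 HDMP + ofatumumab infusions precede the contraception date and 7-8 precede the next scheduled test

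*Combined protocol and SAP*

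**What the plan says.** **Tests.** In the grid of section 2, the row "Pregnancy testing" is marked at screening, in cycle 4 and in cycles 5-12. It is empty for cycle 1 and for cycles 2-3. Footnote 8 and Appendix A set two tests before lenalidomide is prescribed: one 10 to 14 days ahead "and again within 24 hours prior to prescribing lenalidomide for Cycle 1 (prescriptions must be filled within 7 days". After that come "pregnancy tests weekly for the first 28 days of lenalidomide treatment", then tests every 28 days (14 if menses are irregular), at lenalidomide discontinuation and afterwards. Footnote 5 equates the first lenalidomide cycle with protocol cycle 4. Screening may be up to 28 days before the first dose, and under footnote 12 standard-of-care tests done "within 28 days of starting study treatment may be used for screening and do not need to be repeated".

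**Contraception.** Inclusion criterion 11 requires it "at least 28 days before she starts taking lenalidomide". Appendix A lists its periods as "for at least 28 days before starting lenalidomide; 2) throughout the entire duration of lenalidomide treatment; 3) during dose interruptions", and then at least 28 days after lenalidomide stops.

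**For-cause rule.** Appendix A adds: "Pregnancy testing and counseling must be performed if a patient misses her period", or if a test or her bleeding is abnormal.

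**Rules not limited to lenalidomide.** Exclusion 2 keeps pregnant women out. Section 5.7 ends treatment on pregnancy or a positive test. Section 6.2.5 has any pregnancy during participation reported to the ofatumumab supplier. Appendix A also states: "Females must agree to abstain from breastfeeding during study participation and for at least 28 days after lenalidomide discontinuation".

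**The concern.** Women of childbearing potential are eligible, and the induction (eight infusions of HDMP 1 g/m² with ofatumumab) is finished before lenalidomide begins. The plan treats pregnancy as a bar to entry and as a reason to stop treatment. It schedules nothing in cycles 1-3 to prevent or detect one.

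A pregnancy begun between the screening test and the contraception date would breach no contraception rule. At the earliest scheduled test it would be found when induction is nearly or fully over. The woman would then come off treatment under 5.7, after most of the exposure that an earlier test could have avoided.

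A woman who stops during cycles 1-3, or who is removed for progression after cycle 3 (section 5.1), may never reach the lenalidomide rules. Footnote 15 leaves testing at discontinuation to the physician. The safety assessment 28 days after the last dose (footnote 9) names no pregnancy test.

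**Working it through.** **Inputs.** Table 1 (28-day cycles, infusion days and doses); section 5.5.3 (lenalidomide from cycle 4 day 1); criterion 11 and Appendix A (28 days; 10-14 days); footnote 11 (consider prescribing 5-7 days early); footnote 13 (cycle 4 up to 14 days after the cycle 3 marrow); footnotes 3 and 4 (marrow and CT on cycle 3 days 21-28). Dates are nominal and ignore the visit window of ±3 business days.

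**1. Reproduce the calendar.** Study day = 28 × (cycle − 1) + day. The infusions fall on days 1, 8, 15, 22, 29, 43, 57 and 71, that is weeks 1, 2, 3, 4, 5, 7, 9 and 11. Cycle 4 day 1 is 28 × 3 + 1 = day 85, week 13. This matches Table 1.

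**2. Contraception date.** 85 − 28 = day 57. Infusions before day 57: six (days 1 to 43), and the seventh falls on that day. Dose already given: ofatumumab 300 + 5 × 2000 = 10,300 mg; HDMP 6 × 1 = 6 g/m². Latest cycle 4 start: marrow on day 56 + 28 = 84, plus 14 = day 98. Contraception is then due on 98 − 28 = day 70, after seven infusions.

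**3. Next scheduled test** (prescribing day minus 14 to minus 10).

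| Lenalidomide prescribed | Test falls on | Infusions already given |
|---|---|---|
| Day 85 | 71-75 | 7 (if on day 71, before that dose) or 8 |
| Days 78-80 (5-7 days early) | 64-70 | 7 |
| Day 98 (latest start) | 84-88 | 8 |

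All eight infusions amount to 300 + 7 × 2000 = 14,300 mg ofatumumab and 8 g/m² HDMP.

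**4. Interval without a scheduled test.** From day 1: 71 − 1 = 70 to 75 − 1 = 74 days nominally, and 64 − 1 = 63 to 88 − 1 = 87 across the table. From a screening test 28 days before day 1, add 28: 98-102 days nominally, 91-115 overall.

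**5. The for-cause test.** It can apply in cycles 1-3, but it depends on a menstrual signal. Section 3.3.1 lists amenorrhea and menstrual irregularities among methylprednisolone effects. Footnote 8 itself provides for women with no or irregular menstruation, in whom the signal may be absent.

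**6. How many women.** The documents give no figure. Assume that 1% to 5% of the 45 patients are women of childbearing potential: 45 × 0.01 = 0.45 to 45 × 0.05 = 2.25 women. The chance of enrolling at least one is 1 − 0.99^45 = 0.36 to 1 − 0.95^45 = 0.90.

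**7. Contraception after ofatumumab.** None is set for a woman who leaves before lenalidomide. With the half-life range in the ofatumumab pharmacokinetics section (2.3 to 61.5 days, mean about 14), the share of a dose left after 28 days is 0.5^(28/2.3) ≈ 0.02% to 0.5^(28/61.5) ≈ 73%, and 0.5^(28/14) = 25% at the mean. The range is too wide to set an interval from these documents.

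**The case against.** **No fetal risk is stated for the induction drugs.** Neither the ofatumumab nor the methylprednisolone adverse-event section names one, no washout is given, and Appendix A attributes the teratogenic concern to lenalidomide. This stands. A reader might infer that the plan exposes women to a known fetal hazard; the documents do not support that, and the harm cannot be sized from them.

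**Some pregnancy wording concerns lenalidomide alone.** Exclusion 2 adds a parenthesis about not breast-feeding while on lenalidomide, Appendix A says that lenalidomide is stopped on a positive test, and 6.2.5 is a reporting duty. This stands in part. What remains is the bar on pregnancy at entry and 5.7, which ends all study treatment.

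**A test is required in cycles 1-3.** It would be wrong to read the gap as the absence of any required test, because the for-cause rule applies during study participation. The gap is in scheduled tests.

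**Entry safeguards exist.** All participants register in REMS at screening, investigators must ensure compliance with pregnancy risk minimization, and 28 days is a minimum. What REMS asks between registration and prescribing is not in the documents, so its effect in cycles 1-3 can be neither counted nor ruled out. Nothing in the text requires contraception before day 57.

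**Footnote 8 says Cycle 1.** Read literally, this might place the tests before the first infusion. No lenalidomide is prescribed then, and footnote 5 identifies the cycle meant. Contraception stays tied to starting lenalidomide on either reading.

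**Conclusion.** The point holds as a gap in cover during cycles 1-3. On the nominal calendar, six of eight infusions precede the contraception date (seven with a day 98 start), and seven or eight precede the next scheduled test. No scheduled test can trigger 5.7 until induction is nearly or fully complete. The lenalidomide safeguards themselves are complete.

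The importance is modest. Few women are likely to be affected: section 3.1 gives a median age at diagnosis of 72, and the 1-5% share is an assumption. The 36% to 90% is the chance of enrolling such a woman; a reader might take it for the chance of a pregnancy, but no pregnancy rate enters it.

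A reader might also expect the end-of-cycle-3 CT to come before the first test. On the nominal schedule it does not (test on days 71-75, CT on days 77-84); that order can arise only if prescribing is delayed.

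Under 10.4 a woman who leaves before response evaluation counts as a non-responder, which is ordinary conservative handling. The alpha and power of the two-stage design are unaffected. The case for change is patient safety at low cost.

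**What to change.** Keep every lenalidomide rule. Then:

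- In criterion 11 and Appendix A, require effective contraception or abstinence from the first HDMP + ofatumumab dose.
- In the grid and footnote 8, add a pregnancy test within 7 days before cycle 1 day 1 and on day 1 of cycles 2 and 3, with infusion only if negative.
- Add one test at discontinuation for women who leave before lenalidomide.
- In footnote 8, name the first lenalidomide cycle as protocol cycle 4.

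With the first two changes, none of the eight infusions would precede the contraception rule or the first added test. If the sponsor judges that neither induction drug needs this precaution, a sentence giving the reason would close the point. Whether contraception should continue for a time after the last ofatumumab dose is a question for the investigator brochure.

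**Cost.** Three extra tests per woman of childbearing potential, those in cycles 2 and 3 at existing infusion visits. Under the 1-5% assumption that is 3 × 0.45 = 1.35 to 3 × 2.25 = 6.75, or about one to seven tests in the whole trial, plus one for each such woman who leaves early. Contraception starts 57 − 1 = 56 days (8 weeks) sooner. Dosing, endpoints and sample size do not change.

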### 3 Background and Rationale

#### 3.1 Introduction: Chronic lymphocytic leukemia / Small lymphocytic lymphoma

Chronic lymphocytic leukemia (CLL), a monoclonal B-cell malignancy with a low level of proliferation, is characterized by a progressive accumulation of mature-appearing but functionally incompetent, malignant B lymphocytes. CLL is the most common form of leukemia diagnosed in the Western countries. It accounts for over 15,000 new diagnoses (almost 40% of all leukemias) and over 4,000 deaths per year in the United States. CLL is a disease of the elderly with a median age at diagnosis of 72 years and more than two-thirds of patients are over 65 years of age.

The cells are characterized by having mature B-cell markers such as CD19, CD20, and CD22 but also express CD5 which is a T-cell marker. The spectrum of this disease varies from a simple lymphocytosis to splenomegaly and/or cytopenias. Some patients have an indolent course while others have a more accelerated course. In either case, the disease relapses frequently once treatment is initiated, and there is considerable morbidity from the disease and the treatments themselves.

Several predictive factors have been identified in CLL. In addition to clinical staging, traditional prognostic factors for identifying high risk of disease progression have included elevated serum levels of beta-2 microglobulin, soluble CD23, diffuse bone marrow infiltration, short lymphocyte doubling time, and high levels of zeta-associated protein (ZAP-70) on the surface of malignant cells. More recently, the presence of certain cytogenetic abnormalities identified by fluorescence in situ hybridization (FISH) analysis and mutational status of immunoglobulin heavy chain (IgHV) have become a more meaningful predictor of disease progression and duration of response to therapy.

CLL remains non curable by current treatment options with the possible exception of allogeneic hematopoietic stem cell transplantation. Previously, when the need for treatment was established, chlorambucil with or without corticosteroids was often used as

Amendment 5 Dated 03/02/2016

---

first line treatment and purine analogues such as fludarabine as second line treatment. However, first line treatment in most centers is either fludarabine combined with cyclophosphamide or these 2 compounds combined with rituximab. Other treatment options include combination chemotherapy or alemtuzumab. Previously, rituximab has been administered as monotherapy, but due to the low response rates this treatment is now abandoned. Despite having a first line combination regimen of fludarabine, cyclophosphamide and rituximab with an excellent complete response rate of 44%, these patients do relapse and require further treatments. Patients without a complete response also progress and require further therapy. Considering that the vast majority of patients diagnosed with CLL are older than 65 years of age, there is a need to search for a non-chemotherapeutic regimen that provides high efficacy with less toxicity than conventional regimens. We are proposing a combination regimen consisting of high dose methylprednisolone combined with ofatumumab, followed by consolidative therapy with lenalidomide in combination with ofatumumab (See Section 1 Table 1 for dosing schema and details of regimen).

### **3.2 Ofatumumab**

Ofatumumab (Arzerra®) is a human monoclonal antibody that targets a unique small-loop epitope on CD20 and elicits potent *in vitro* complement-dependent cytotoxicity, even in malignant B cells with low levels of CD20 expression. Ofatumumab is currently approved by the FDA for fludarabine and alemtuzumab refractory CLL. It is also under development by Novartis for the treatment of untreated, relapsed or refractory B-cell follicular lymphoma, for the treatment of untreated CLL, for the treatment of active rheumatoid arthritis, and other autoimmune diseases.

#### **3.2.1 Ofatumumab Indications**

Ofatumumab was approved by the FDA on October 27th, 2009 for the treatment of patients with CLL whose cancer is no longer being controlled by other forms of chemotherapy. It has also shown potential in treating follicular non-Hodgkin's lymphoma

(FL), diffuse large B cell lymphoma, rheumatoid arthritis (RA) and relapsing remitting multiple sclerosis.

